### **Feasibility:**

The study is feasible for enrollment over 9 months, with 3 months follow-up for efficacy based on volume of the clinics at UF. Specifically, the three adult GI providers at UF Health who will be participating in this trial will enroll patients from 10 clinics/wk, which represents approximately 150 patient visits/wk. Of these, approximately 40% of patients are being seen for peptic acid/GERD indications which should produce 50-60 pts/week who meet inclusion criteria. Assuming only half of eligible patients consent to the study, we anticipate enrolling the 120 adults within a 12 week period.

### **Analysis Plan and Power Calculations:**

We will test the hypothesis that RMs/UMs (1 or 2 gain-of-function alleles) in the genotype-supported arm have better GERD and symptom control than RMs/UMs in the conventional treatment group because they will have their dose increased based on their genotype.

Continuous variables will be compared between the genotype-supported group and the conventional treatment group using the Student's unpaired *t*-test, and categorical variables will be compared using the chi-square or Fisher's exact test. The hypotheses will be tested using linear regression analysis to estimate the difference in the RDQ reduction in the RM/UM patients between the two arms. All analysis will be performed in SAS 9.4 (Cary, NC).

We will evaluate the percentage of the time when a dosing recommendation was made and accepted by the treating clinician, to provide practical data on the willingness of clinicians to adopt this approach. We will also collect patient- and provider-level survey data on knowledge, attitudes, and beliefs about pharmacogenetics testing, using survey tools adapted from other IRB-approved studies.

Power calculation. While there are no data in the literature on genotype associations with the efficacy endpoint we will use (symptom improvement), there are pH probe data by genotype that were generated by the Nemours investigators, that we can use, and this should be an excellent surrogate for symptom data. We have done power calculations based on two of the pH-based response phenotypes, found in Table 3. Specifically we powered based on percent time with pH < 4 (which has an effect size of 0.79) and acid clearance time (effect size of

0.45). Based on these two phenotypes, we have the following power to detect differences in efficacy between *CYP2C19\*17* carriers and non-carriers:

Based on the previous data for acid clearance time, with 180 total participants (120 from UF Health and 60 from Nemours), we have 81% power to detect a 0.49 effect size.

Based on the previous data for time with pH <4.0, with 180 participants, we have >99% power to detect a 0.79 effect size.

With 180 total patients (90 patients in each arm), we expect approximately 30 patients in each arm to have the genotype of interest (i.e. RM or UM). At alpha of 0.05, we will have 80% power to detect effect size of  $\geq 0.74$  in the RDQ score in RMs/UMs. This effect size is equivalent to a RDQ score difference of 1.22 for regurgitation and a score difference of 0.93 for heart burn. These differences in RDQ scores are smaller than what is considered clinically significant. Therefore our study is well-powered.

In summary, by studying a total 180 patients (120 from UF Health and 60 from Nemours), the data suggest we will have excellent power to detect an efficacy endpoint. Data generated from this protocol on adverse effects will also help us define the incidence of the adverse effect phenotypes to inform sample size for a future pragmatic trial examining effects of genotype-supported dosing on PPI safety endpoints.

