## 7. Research Plan:

The study is a randomized, open-label, comparative effectiveness clinical trial in 180 total patients with GERD or dyspepsia symptoms who will be randomized to either conventional or genotype-supported treatment of GERD and dyspepsia. A total of 120 patients will be enrolled in the UF Health Gastroenterology Clinics in Gainesville, and 60 will be enrolled in a parallel study (under separate IRB protocol) at Nemours Children's Hospital Gastroenterology Clinics in Orlando, FL. Each site will be responsible for overseeing patient care and research at their respective facility. All participants will have symptoms of GERD or related diseases and be candidates for PPI therapy or on PPI therapy with continued symptoms.

We will enroll a total of 180 patients between the UF Health and Nemours sites, which should allow for sufficient power to detect our efficacy endpoint (see power calculation below). We will also collect data from the health records for up to 24 months after enrollment on upper respiratory infection (cold), sore throat, strep throat, bronchitis, pneumonia, ear infection, acute sinusitis (sinus infection), bone fractures, renal function, and gastrointestinal infections for preliminary assessment of the effects of *CYP2C19*-supported PPI dosing on adverse effects. This exploratory arm will provide data to inform power calculations for a larger study focused on preventing PPI-associated adverse events through genotype-supported dosing.

**Inclusion Criteria.** A total of 120 patients with GERD or related symptoms will be enrolled at UF Health. An additional 60 patients will be enrolled at Nemours Children's Hospital Gastroenterology Clinics under a separate IRB protocol. For this protocol, any patient over the age of 17 who presents to GI clinic with GERD or related symptoms and is either 1) being initiated on PPI therapy or 2) continues to have symptoms despite PPI therapy will be considered eligible for the study.

Exclusion Criteria. This study will exclude patients who have had extensive esophageal or gastric surgery or any major chronic illness or condition that in the opinion of the gastroenterologist that would interfere with participation in the study.

Participant Recruitment Methods.

Prior to enrolling their patients, clinicians at participating GI clinics (investigators for this study) will be asked to complete surveys that assess their knowledge, attitudes, and beliefs as they relate to pharmacogenetics testing.

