Patients will be approached for participation at their GI clinic visit by the treating clinician and/or physician assistant. After providing informed consent, patients will be randomly assigned to either conventional treatment or genotype-supported PPI therapy using a randomization table. A 5-ml (one teaspoon) venous blood sample will then be drawn by a nurse, physician assistant, or phlebotomist. The patient will be asked to complete 3 surveys/questionnaires: the Reflux Disease Questionnaire (RDQ), Global Overall Symptom (GOS) scale, and a survey to assess knowledge, attitudes, and beliefs about pharmacogenetic testing. Patients will receive a total of \$25 for participating in this study. The \$25 VISA gift card will be provided after completing the final questionnaire. Patients in the control group may be withdrawn prior to completion if they or their physician elect to order the genetic test during the study. These patients would receive a \$10 VISA gift card for their participation up to the point of withdrawal.

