Assessment of PPI efficacy and adverse effects. Our primary outcome will be the effectiveness of PPI therapy, which will be determined via two questionnaires: RDQ and GOS scale, administered by study personnel at baseline and 12 weeks. The RDQ was developed to monitor treatment response over time and evaluates 6 symptoms (12 items) covering 3 domains: heartburn, regurgitation, and upper abdominal pain. Each symptom is evaluated using a 6-point Likert scale to assess frequency and severity over the previous week. Each symptom is rated from 1 (did not have) to 6 (severe), and the RDQ mean score is calculated as the mean response to the 12 items. The RDQ mean score thus ranges from 1 to 6 and has been psychometrically validated. The GOS scale evaluates 18 symptoms, with each rated from 1 (no problem) to 7 (very severe). Similar to the RDQ, the mean score is calculated as the mean response to the 18 items, with mean scores ranging from 1 to 7. Patient participation will end after they complete the approximate 12 week questionnaire. However, we will continue to

follow patients over 24 months through medical record review to assess adverse outcomes for occurrence of upper respiratory infection (cold), sore throat, strep throat, bronchitis, pneumonia, ear infection, acute sinusitis (sinus infection), bone fractures, renal function and gastrointestinal infections.

Metrics for assessing success of pharmacogenetic testing in clinical practice. We will test a variety of variables that will provide insight into attitudes and acceptability of pharmacogenetic testing. These will include: 1) percent of patients approached about the study who agree to participate; 2) surveys of patients and clinic staff on knowledge, attitudes, and beliefs about pharmacogenetic testing; and 3) the percent of the time a dosing recommendation for a patient in the genotype-supported arm is accepted by the clinician. Patients will be surveyed about knowledge, attitudes, and beliefs about pharmacogenetic testing using questionnaires on enrollment and at the end of their study participation. Clinic staff will be surveyed about knowledge, attitudes, and beliefs about testing at the beginning and end of the study.

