Genetic results and clinical decision support. Results will be entered in the participant's electronic health record; genotype results for participants in the control/conventional arm will not be made available to patients/families through the secure patient portal in the EMR to maintain blind status. PPI recommended dosing will be made available to GI providers in the EMR for genotype-guided dosing. PPI templates will include phenotype, genotype, dosing recommendations, and educational information. Participants in the conventional arm will be prescribed the conventional PPI dose.

To minimize risks associated with genetic studies, all results of genetic tests and patient data will be stored in a secure database which is accessible only to study investigators. Genotype and phenotype data will be stripped of all identifiers prior to submission to the NIH dbGAP repository.

Assessment of PPI adverse events and efficacy. Our primary outcome will be a directed interview and questionnaire by study personnel at baseline and every following week up to 12 weeks of participation for efficacy of PPI therapy and for adverse outcomes for the study period: upper respiratory infection (cold), sore throat, strep throat, bronchitis, pneumonia, ear infection, acute sinusitis (sinus infection), and gastroenteritis. We have experience using the questionnaire to evaluate the safety of PPI treatment in children. The prevalence of each respiratory and gastrointestinal symptom will be compared in participants receiving conventional vs. genotype-supported dosing. As secondary outcomes, the efficacy and safety (adverse event score) of PPI therapy will be determined from scores from patient and parent-proxy reported outcomes: the GASP-Q, the validated SN-5 Pediatric Sinonasal Symptom Survey and validated PedsQL™ Gastrointestinal Symptoms Module. Efficacy and adverse events questionnaires will be completed via an electronic questionnaire on a weekly basis and stored in REDCap.

At Nemours Children's Hospital continuous monitoring on study metrics will be offered by study staff. Study metrics will include Gasp-Q, PedsQL™ Gastrointestinal Symptoms Module, SN-5 Pediatric Sinonasal Symptom Survey and Safety Q.

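### The RDQ change-score regression names no covariates although baseline RDQ and PPI status at entry are known, and nothing requires the baseline questionnaires to be completed before the open-label arm is disclosed

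*Combined protocol and SAP*

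**What the plan says.** In the UF protocol, section 7, Analysis Plan and Power Calculations, the RDQ hypothesis has one sentence: "The hypotheses will be tested using linear regression analysis to estimate the difference in the RDQ reduction in the RM/UM patients between the two arms". For other continuous comparisons: "Continuous variables will be compared between the genotype-supported group and the conventional treatment group using the Student's unpaired *t*-test". Neither sentence names a covariate. On numbers, the same section says "we expect approximately 30 patients in each arm to have the genotype of interest", and it claims 80% power at alpha 0.05 for an effect size of at least 0.74.

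Two baseline variables will be in hand. The efficacy assessment uses "RDQ and GOS scale, administered by study personnel at baseline and 12 weeks". The inclusion criteria admit adults who are either "being initiated on PPI therapy or 2) continues to have symptoms despite PPI therapy will be considered eligible for the study", so PPI status at entry is known for every adult.

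On the order of events, Participant Recruitment Methods says that after consent "patients will be randomly assigned to either conventional treatment or genotype-supported PPI therapy using a randomization table". It then describes the blood draw, and after that: "The patient will be asked to complete 3 surveys/questionnaires". RDQ and GOS are two of the three. The Research Plan describes the trial as open-label.

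The only sentence about covariates is in the statistical analysis paragraph of the Nemours text. It concerns multivariable models of events and selects covariates by their significance. It does not cover the RDQ regression.

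**The concern.** A change score subtracts the whole baseline value, whatever the correlation between visits. When that correlation is moderate, this adds noise that regression on baseline would remove. The loss falls on a genotype subgroup planned at about 30 per arm, where the claimed power is 80% with no allowance for dropout or for the control-arm withdrawals the protocol foresees. Because the plan does not say which covariates enter the model, that choice can be made after the data are seen. The Data Safety Monitoring Plan makes this a practical matter, since the investigator team is to analyse data as they accumulate.

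The order of steps is a separate matter but linked. RDQ and GOS are self-reported. If a patient knows the arm when giving the baseline answers, any resulting shift goes in full into the change score. It also contaminates the variable one would adjust for, so baseline RDQ is a safe covariate only if it is recorded first.

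**Working it through.** **Inputs from the documents.** 180 patients, 90 per arm. RM plus UM frequency from Table 1: 28% + 5.3% = 33.3%, so 90 × 0.333 ≈ 30 per arm. Alpha 0.05 (sidedness not stated), effect size 0.74, power 80%.

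**Reproducing the plan's figure.** Two-sided two-sample t-test, 30 per arm, d = 0.74, 58 df: power 80.5%, and detectable effect at 80% power 0.736. The normal approximation gives 81.8%. A one-sided t-test gives 88.2% and does not match. The stated power is therefore that of an unadjusted two-sided comparison. It leaves no slack: at 29 per arm the detectable effect is about 0.736 × √(30/29) = 0.749, already above 0.74.

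**Effect of adjusting for baseline RDQ.** The documents give neither the baseline-to-week-12 correlation ρ nor the SDs. Assume equal SDs σ at both visits and ρ of 0.3, 0.5 or 0.7.

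- Change score: variance 2σ²(1 − ρ).
- ANCOVA residual: variance σ²(1 − ρ²).
- Ratio ANCOVA/change: (1 − ρ²) / [2(1 − ρ)] = (1 + ρ)/2.

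Reading 0.74 in change-score SDs, power follows from the noncentral t with d/√ratio and 56 df (two covariates fitted):

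| | Unadjusted | ρ = 0.3 | ρ = 0.5 | ρ = 0.7 |
|---|---|---|---|---|
| Variance ratio | 1 | 0.65 | 0.75 | 0.85 |
| Power, 30 per arm | 80.5% | 93.7% | 90.2% | 86.3% |
| Power by simulation (8,000 runs; baseline plus a binary covariate with no effect) | about 80.5% | 93.1% | 89.2% | 85.3% |
| Detectable effect, 30 per arm | 0.74 | 0.59 | 0.64 | 0.68 |
| Power, 20 per arm | 62.6% | 80.6% | 74.8% | 69.5% |
| Detectable effect, 20 per arm | 0.91 | 0.73 | 0.79 | 0.84 |

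The 20-per-arm rows apply if only UF adults contribute RDQ: 120 × 0.333 / 2 ≈ 20. The Nemours text lists other instruments ("the GASP-Q, the validated SN-5 Pediatric Sinonasal Symptom Survey and validated PedsQL" GI module) and no RDQ.

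**Sensitivity to the scale of 0.74.** If 0.74 is in SDs of the raw RDQ score, the change-score analysis has 66%, 80.5% or 95% power for ρ = 0.3, 0.5 or 0.7, against 84%, 90% or 98% with ANCOVA.

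**Sensitivity to unequal SDs.** With q = week-12 SD / baseline SD, the ratio is q²(1 − ρ²) / (1 + q² − 2ρq). At ρ = 0.5:

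- q = 0.8: 0.48/0.84 = 0.571, a 43% variance reduction.
- q = 1.25: 1.172/1.3125 = 0.893, an 11% reduction.
- q = 2: 3/3 = 1, no gain.

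**PPI status at entry.** The documents give nothing from which to compute a gain.

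**Timing, as illustration only.** Suppose knowing the arm shifts baseline in one arm by s = 0.2 baseline SDs. The change score is biased by s = 0.20. ANCOVA is biased by ρqs, which with q = 1 is 0.06, 0.10 or 0.14. To set these against 0.74 in change-score SDs, divide by √[2(1 − ρ)] = 1.18, 1.00 or 0.77. That gives 0.17, 0.20 or 0.26 for the change score and 0.05, 0.10 or 0.18 for ANCOVA.

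**The case against.** The case against is that the plan contains no error here. The unadjusted change score is valid, the 80% reproduces, and naming linear regression alongside the t-test leaves room for covariates. The plan also says its detectable differences are below what is clinically significant, which amounts to claiming a margin. The gains rest on an unknown ρ, and they shrink or vanish if the week-12 SD is much larger than the baseline SD. On timing, the text attaches an explicit order only to the blood draw. The RDQ asks about the previous week, and genotype results take about two weeks, so no genotype-based dose change can precede baseline. The proposed model also leaves out site, although the 30 per arm pools two sites.

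Much of this is right as far as it goes. The point is not that the analysis is invalid or that the power figure is wrong. But room for covariates is not prespecification. The margin claim rests on a cited source that cannot be checked here, and it concerns clinical relevance rather than lost patients. Under either reading of 0.74, ANCOVA has the higher power across the assumed range of ρ with equal SDs. Where SDs make the gain zero, as at q = 2 and ρ = 0.5, the cost is only the degrees of freedom; there the timing bias is not reduced either, since ρq = 1. The two-week turnaround rules out an early dose change but not a change in how patients report. The site comment stands if the two sites' RDQ data are pooled.

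**Conclusion.** The concern holds, as a precision and prespecification point together with an unguarded step in the enrolment sequence. With equal SDs, ρ between 0.3 and 0.7, and 0.74 in change-score SDs, prespecified baseline adjustment takes power at 30 per arm from 80.5% to between 86% and 94%. Equivalently, it lowers the detectable effect by about 0.06 to 0.15 SD. With unequal SDs the gain may be larger, smaller or nil, and the contribution of PPI status is unknown. If RDQ comes from UF adults only, adjustment recovers part of the lost power and reaches 80% only near ρ = 0.3. The timing risk is possible, not shown: the documents do not say when patients learn their arm, and the 0.2-SD shift is assumed. Adjustment does not reliably remove such a shift; fixing the order does. The change should be made, but leaving the plan as it stands would not invalidate the comparison.

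**What to change.** In Analysis Plan and Power Calculations, name the primary model: week-12 RDQ mean score regressed on arm, baseline RDQ mean score and PPI status at entry (new start or continuing), in RM/UM patients. State that GOS is analysed the same way with its own baseline. If RDQ data from the two sites are pooled, add site. In Participant Recruitment Methods, state that RDQ and GOS are completed before the assignment is opened.

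The cost is one sentence in the analysis plan, a reordered visit checklist and two degrees of freedom (one more if site is included). No new data are collected and the sample size need not change.

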Mean Number Acid Reflux Episodes(SD) in 24 hrs	25(35)	24(32)	0.71-1.5	NS

\*GOF = Gain-of-function--\*17 carriers, LOF = Loss-of-function carriers + no variant alleles

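### The 81% and >99% efficacy power figures belong to paediatric pH-probe effect sizes, not to the RDQ comparison; that comparison has about 40% power at the plan's own 0.45

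*Combined protocol and SAP*

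**What the plan says.** Under Analysis Plan and Power Calculations (section 7 of the UF protocol), the hypothesis concerns RM/UM patients. Linear regression is to estimate the between-arm difference in RDQ reduction in that subgroup.

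The power paragraph then concedes that no published data link genotype to symptom improvement. It turns to pH-probe data from the paediatric site, with the comment that "this should be an excellent surrogate for symptom data", and continues: "We have done power calculations based on two of the pH-based response phenotypes, found in Table 3". The two measures are "percent time with pH < 4 (which has an effect size of 0.79" and acid clearance time, given first as 0.45 and then as 0.49. For a comparison of gain-of-function carriers with non-carriers among 180 participants, the section reports 81% power for acid clearance and >99% for time with pH below 4, and describes both as power for differences in efficacy.

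A separate calculation follows for the RDQ, with about 30 RM/UM patients in each arm: "At alpha of 0.05, we will have 80% power to detect effect size of" 0.74 or more. The section converts this to RDQ points (1.22 for regurgitation, 0.93 for heartburn). Its summary is that "the data suggest we will have excellent power to detect an efficacy endpoint".

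Table 3 (preliminary data, 21 versus 53 children) has a third pH-probe row that the power section does not use: "Mean Number Acid Reflux Episodes(SD) in 24 hrs", 25 (35) versus 24 (32), marked not significant.

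**The concern.** Power belongs to an endpoint, a contrast and an effect size together. The 81% and >99% figures take their effect sizes from a different measurement, made in children, for a different contrast (carriers versus non-carriers rather than arm versus arm within RM/UM). No pH monitoring appears among the efficacy assessments that either protocol lists. The documents give no correlation or other evidence linking pH-probe change to RDQ change, so the strength claimed for the surrogate is asserted and not shown. The background section itself names adherence and oesophageal hypersensitivity, alongside drug metabolism, as contributors to refractory GERD. That is a reason not to assume that a pH effect passes through to symptoms at full size.

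The choice of two outcomes from three adds to this. Both chosen outcomes were significant, the one left out was not, and no reason is given.

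What is at stake is how a null RDQ result would be read. Next to a printed >99%, it looks like strong evidence of no benefit. If power for the tested comparison is nearer 40% at a moderate effect, a null result says much less.

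**Working it through.** **Inputs.** 180 participants and about 30 RM/UM per arm, so about 60 carriers and 120 non-carriers (power section). Effect sizes 0.45, 0.49, 0.79 and 0.74 (power section). Means, SDs and group sizes from Table 3. The named comparison is "using the Student's unpaired *t*-test". Alpha is 0.05 for the RDQ calculation; none is stated for the pH calculations, so 0.05 is assumed. Sidedness is not stated; two-sided is assumed throughout.

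**Formula.** Power is the noncentral-t probability beyond the critical value, with noncentrality δ = d × √(n1·n2/(n1+n2)) and n1+n2−2 degrees of freedom.

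1. *The plan's pH figures, 60 versus 120.* √(60×120/180) = 6.32.
   - d = 0.45: δ = 2.85, power 80.8%. This matches the printed 81%.
   - d = 0.79: δ = 5.00, power 99.9%. This matches >99%.
   - d = 0.49, the value printed beside 81%: δ = 3.10, power 86.9%. The 81% therefore goes with 0.45, not 0.49.

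2. *The plan's RDQ figure, 30 versus 30.* √(30×30/60) = 3.87.
   - d = 0.74: δ = 2.87, power 80.5%. The effect detectable with 80% power is 0.736. The plan's statement is correct.

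3. *The plan's pH effect sizes placed in the tested comparison, 30 versus 30.*
   - d = 0.45: δ = 1.74, power 40%.
   - d = 0.49: δ = 1.90, power 46%.
   - d = 0.79: δ = 3.06, power 85%.

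   This step is an illustration. A carrier versus non-carrier difference would carry over unchanged as an arm effect within RM/UM only if genotype-supported treatment closed the whole gap and the standardised effect were the same on the RDQ.

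4. *The unused Table 3 outcome.* Pooled SD = √((20×35² + 52×32²)/72) = √(77,748/72) = 32.9, so d = (25 − 24)/32.9 = 0.03. Its standard error is about √(1/21 + 1/53) = 0.258, so the 95% CI is 0.03 ± 1.96 × 0.258, about −0.48 to 0.54. The interval contains 0.45 and 0.49 but not 0.79.

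5. *Can the other two Table 3 effects be checked?* For acid clearance the pooled SD is √((20×271² + 52×158²)/72) = 196, so d = (181 − 107)/196 = 0.38, which is neither 0.45 nor 0.49. For time with pH below 4 the table gives no SD; 0.79 implies an SD of (5.71 − 2.67)/0.79 = 3.85. The acid-clearance discrepancy is a separate matter, and the present point would remain if it were corrected.

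**The case against.** The plan is open about what it did. It says that no symptom data by genotype exist, calls the pH data a surrogate, says that it used two outcomes, and points to a table that prints the third row in full. A reader might infer concealment; the documents do not support that.

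A reader might also infer that the efficacy power rests on pH data alone. It does not. The optimistic summary comes after the RDQ calculation, which is on the tested contrast and reproduces. The plan adds that the detectable RDQ differences are smaller than what counts as clinically significant. That speaks to relevance, although the threshold itself is not printed.

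A third tempting reading is that the trial has 5% power, because that is what d = 0.03 gives with 60 versus 120. This should not be quoted. Power at any near-zero effect is close to alpha by construction, and the interval around 0.03 is wide enough to include 0.45. Different pH outcomes can also have different true effects. The description of Table 3 in the preliminary data uses time with pH below 4 as its example of poorer response, so preferring that measure is not arbitrary.

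All of this stands, and it limits the point. It does not make 81% or >99% a power for the RDQ. The RDQ calculation shows what could be detected and gives no reason to expect an effect that large. 80% power at 0.74 does not by itself justify the word excellent.

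**Conclusion.** The point holds in this form: 81% and >99% are powers for pH-probe effect sizes and should not stand as power for efficacy in this trial. For the tested comparison the supportable statement is 80% power at a standardised RDQ difference of about 0.74. The same comparison has about 40% power at 0.45 and about 85% at 0.79, and no document shows which of these, if any, is the likely symptom effect. The unused reflux-episode outcome (0.03, about −0.48 to 0.54) supports one limited conclusion: the three pH outcomes do not agree on a single effect to transfer. It does not show that genotype has no effect, or that the trial's power is 5%.

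These figures assume two-sided 0.05, equal arms, and 30 analysable RM/UM per arm. The plan states no dropout allowance. If 10% or 20% were lost (assumed; 27 or 24 per arm), power at 0.74 would be 76% or 71%. The 30 per arm also counts the 60 children, whose listed efficacy instruments do not include the RDQ. If only the 120 adults supplied RDQ data (assumed one third RM/UM, 20 per arm), power at 0.74 would be 63% and the effect detectable with 80% power would be 0.91.

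**What to change.** In the power section of the UF protocol:

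- Remove the 81% and >99% figures as power for efficacy.
- Keep the RDQ calculation as the sole power statement, and state its sidedness and the number of analysable RM/UM per arm on which it depends.
- Replace the closing claim of excellent power with that figure, for example: *With about 30 RM/UM per arm and two-sided alpha 0.05, the comparison of RDQ reduction has 80% power for a standardised difference of 0.74. The size of the symptom effect of genotype-supported treatment is unknown.*
- If the pH data stay as rationale, show all three Table 3 outcomes, including 0.03 with its interval for reflux episodes, and drop the description of the surrogate as excellent.
- Do not substitute 5% as the trial's power.

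This changes wording only. Sample size, conduct and analysis stay as they are. The cost is a less favourable power statement.

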Table 4 shows *CYP2C19* \*2 (loss-of-function) and \*17 (gain-of-function) allele frequencies in children who were on PPIs and underwent fundoplication surgery compared to controls (consisting of asthmatic patients who participated in the PPI trial). DNA for genotyping was obtained from saliva samples collected from controls, and for cases was obtained from tissue samples collected from children during fundoplication surgery. The frequency of the

CHARACTERISTIC	GOF (N=21)*	LOF (N=53)	RR (CI)	P value
Caucasian, %	76	71		NS
Male, %	66	62		NS
Mean Age at pH test, years(SD)	8(4.6)	8(4.9)		NS
Mean PPI Dose(SD), mg/kg	1.26(0.45)	1.00(0.62)		NS
% time pH < 4	5.71	2.67	1.6 (1.1-2.3)	<0.005
Mean Acid clearance (SD)	181(271)	107(158)	2.2 (1.5-3.2)	<0.0001
Mean Number Acid Reflux	25(35)	24(32)	0.71-1.5	NS
Episodes(SD) in 24 hrs				

\*GOF = Gain-of-function--\*17 carriers, LOF = Loss-of-function carriers + no variant alleles

minor \*2 allele (A allele in Table 4) (PM or IM phenotype) was under-represented in the fundoplication cohort compared to controls, and the minor allele for the \*17 allele (T allele) (RM phenotype) was over-represented in the fundoplication cohort compared to controls. These data suggest that RMs are more likely to be undertreated with usual doses of PPI therapy and as a result are subjected to invasive management approaches. In contrast those with the PM phenotype are effectively treated with a usual dose and so are under-represented in the surgical group. These data could be inferred to suggest that genotype-supported PPI dosing could result in dose increases in RMs, which may have the potential to reduce the number of children who would need to undergo fundoplication surgery.

SNP/GENOTYPE	CONTROL 	FUNDOPLICATION
*2 (rs4244285)	Number (Percent)	Number (Percent)
GG	199 (71.5%)	31 (91.2%)
GA	75 (27.0%)	3 (8.8%)
AA	4 (0.15%)	
MAF	0.149	0.044
p value		0.010
*17 (rs12248560)		
CC	178 (64.0%)	17 (50%)
CT	91 (32.6%)	14 (41%)
TT	10 (3.50%)	3 (9.0%)
MAF	0.200	0.294
p value		0.033

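### The acid-clearance effect size of 0.45 (0.49 where the 81% power is stated) cannot be derived from Table 3, whose means and SDs give 0.38 and about 61–66% power

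*Combined protocol and SAP*

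**What the plan says.** In the protocol's section 7, under Analysis Plan and Power Calculations, the sponsor notes that no genotype data exist for the symptom endpoint and uses pH-probe data as a surrogate: "We have done power calculations based on two of the pH-based response phenotypes, found in Table 3". It continues: "Specifically we powered based on percent time with pH < 4 (which has an effect size of 0.79) and acid clearance time", and gives 0.45 for the latter. The contrast is carriers of the *17 allele against non-carriers. The next paragraph, still referring to the acid-clearance data, states 81% power with 180 participants for an effect size of 0.49.

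Table 3 (section 5, Preliminary Data, repeated in the Nemours text) heads its columns "GOF (N=21)* LOF (N=53" and gives the row as "Mean Acid clearance (SD) 181(271) 107(158"). Its footnote defines the comparison group: "LOF = Loss-of-function carriers + no variant alleles". The same row carries a relative risk of 2.2 (1.5–3.2) and P <0.0001.

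The power section then gives a separate calculation for rapid and ultra-rapid metabolizers (RM/UM) compared between arms: about 30 per arm, effect size 0.74, 80% power. It closes that "the data suggest we will have excellent power to detect an efficacy endpoint".

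**The concern.** A reader who takes the cited means and SDs and forms a standardised difference does not arrive at 0.45, nor at the 0.49 printed with the power. Reconciling those two numbers with each other would not settle the matter, because neither follows from the table.

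Acid clearance is one of two surrogate effects offered in support of 180 participants, and it is the weaker one. If its effect size is overstated, so is the 81%, and the closing statement about power loses part of its basis.

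**Working it through.** **Inputs.** Table 3: means 181 and 107 (difference 74), SDs 271 and 158, N = 21 and 53. Split of the 180: the plan expects about 30 RM/UM in each of two arms, so about 60 carriers and 120 non-carriers. Alpha 0.05; sidedness is not stated, so two-sided is assumed. Test: Student's unpaired t-test, as the plan names.

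**Step 1: reproduce the stated 81%.** The noncentrality is d × √(n₁n₂/(n₁+n₂)) = d × √(60 × 120/180) = 6.325 d, on 178 df.
- d = 0.45: 6.325 × 0.45 = 2.846, power 80.8%.
- d = 0.49: 6.325 × 0.49 = 3.099, power 86.9%.

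So 81% matches 0.45, not the 0.49 printed beside it. Getting 81% at 0.49 needs about 45 carriers and 135 non-carriers (25% carriers). Table 1 gives 28% + 5.3% = 33.3% RM/UM.

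**Step 2: effect size from Table 3.**
- Pooled SD = √[(20 × 271² + 52 × 158²)/72] = √38,430 = 196.0; d = 74/196.0 = 0.377, or 0.38.

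| Standardiser | SD | Effect size |
|---|---|---|
| Carrier SD | 271 | 0.27 |
| Root-mean-square of the two SDs | 221.8 | 0.33 |
| Simple average of the two SDs | 214.5 | 0.345 |
| Pooled SD | 196.0 | 0.38 |
| Non-carrier SD | 158 | 0.47 |

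An effect of 0.45 would need an SD of 74/0.45 = 164, which none of these gives. An effect of 0.49 would need 74/0.49 = 151, below both printed SDs.

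**Step 3: power at the Table 3 effect.**
- d = 0.377, 60 vs 120: 6.325 × 0.377 = 2.387, power 66%.
- Student's t simulated with normal data and SDs of 271 (n = 60) and 158 (n = 120): about 61%.
- Other splits, pooled SD: 51/129 (Table 3's own ratio) 62%; 70/110 (Table 1 with *2/*17 counted as carriers) 69%; 90/90 71%. None reaches 81%.
- For 80% power at 0.3775 with a 1:2 split, about 83 + 166 = 249 participants.

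**Step 4: the separate between-arm calculation.** With 30 per arm and an effect size of 0.74, power is 80.5%. The stated 80% reproduces and does not use the acid-clearance figure.

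**The case against.** **Another scale may lie behind the effect sizes.** The plan says the phenotypes are found in Table 3; it does not say that the effect sizes are differences in means over a pooled SD. Table 3 prints no SD for percent time with pH <4, so 0.79 cannot have been formed that way from the table. Both acid-clearance SDs exceed their means, so the data are probably skewed and a ratio scale is plausible. Also, ln 2.2 = 0.79, the log of the acid-clearance relative risk, although the plan assigns 0.79 to the other phenotype. That phenotype's relative risk of 1.6 has ln 1.6 = 0.47, and values rounding to 1.6 (1.55–1.65) span 0.44–0.50, which contains both 0.45 and 0.49. The effects could therefore be log relative risks with the two rows interchanged. This is conjecture. It stands as a reason not to call 0.38 the only possible value, but it does not rescue the 81%: the documents state no such scale, and a log ratio needs its own SD before it yields power.

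**The non-carrier SD is a recognised standardiser.** It gives 0.47 and about 84% power. It is still not 0.45, and it ignores the larger carrier SD, whereas the named test pools the two.

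**A one-sided test would help.** It gives about 77% at 0.38, but 88% at 0.45, so the stated 81% was evidently not computed that way at this split.

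**Stronger readings that do not hold.** A t-test on the printed means and SDs gives p = 0.15, and a reader might infer that the row's P <0.0001 is wrong. It agrees with the printed relative risk: SE = (ln 3.2 − ln 1.5)/3.92 = 0.193, z = 0.788/0.193 = 4.1. A reader might also put power at 49%, the result of Welch's test with these SDs, but the plan names Student's t. Nor does this show the trial's main comparison to be underpowered. Acid clearance is not an outcome in the adult trial, and carriers against non-carriers is not the randomised contrast.

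**Conclusion.** The point holds as a secondary one. The effect size attached to acid clearance is not supported by the table cited for it. On the printed figures it is 0.38, and power for carriers against non-carriers is about 61–66%, some 15 to 20 percentage points below the stated 81%.

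This rests on a 60/120 split, a two-sided 0.05 test, and raw-scale means and SDs as the basis of the effect. Linking 81% to 0.45 is a back-calculation, since the text attaches it to 0.49. Whether 0.45 has a legitimate source elsewhere cannot be decided from the documents; what can be said is that none is given.

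**What to change.** In the Power calculation paragraphs, use one acid-clearance effect size throughout, and state the split and the sidedness. Then do one of the following:

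1. Restate the effect as 0.38 and the power as about 61–66%.
2. State the scale and source of 0.45/0.49 and recompute the power on that scale. In doing so, check whether the acid-clearance and percent-time rows were interchanged, given that 0.79 equals the log of the acid-clearance relative risk.

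Unless the documented source supports 81%, stop citing acid clearance in support of the closing statement about power. Table 3's P value and the RM/UM between-arm calculation need no change on this account.

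The cost is a text correction and a look back at the pH-probe analysis. Under the first option a stated figure becomes less favourable. Neither option in itself changes the sample size or the analysis of the randomised comparison.
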